5.1.2. Pooling Sites for Analysis

Data from all investigational sites will be pooled for the analysis, unless specified otherwise.

5.1.3. Estimands

Following [International Conference on Harmonisation \(2014\)](#) and [National Research Council \(2010\)](#), the following estimands are considered for efficacy endpoints to provide clarity of what to be estimated and its connection to the trial objectives. [Akacha, et. al. \(2017\)](#) proposed a framework for defining an estimand using three attributes:

- The population of interest;
- The variable to be used for the clinical question, which consists of measurements at a specific timepoint. It could be a composite endpoint that incorporates post-randomization events.
- The measure of intervention effect, which accounts for potential effects of post-randomization events.

A composite estimand will be used for the primary endpoint and a hypothetical estimand will be used for lab parameter defined secondary endpoints. Alternative estimands are also proposed to either assist the interpretation of primary estimand or used for exploratory endpoints.

Composite Estimand

- Population: FAS
- Variable: A composite endpoint: endpoint response criteria, and remain in the study through at least Week 23 visit (i.e., patients who discontinued the study participation prior to Week 23, including those who discontinued prior to Week 5, are considered non-responder)
- Measure of Intervention Effect: Proportion of subjects who respond according to the variable definition

Hypothetical Estimand

- Population: FAS

- Variable: Change from baseline at treatment assessment timepoint (Weeks 23, 25, and 26), where any post-baseline value after transfusion and prohibited medication (from Week 5 to Week 26) is considered missing
- Measure of Intervention Effect: Mean change from baseline, had transfusion and prohibited medications not been available

De-Facto Estimand

- Population: FAS
- Variable: Change from baseline at treatment assessment timepoint (Weeks 23, 25, and 26)
- Measure of Intervention Effect: Mean change from baseline, irrespective of transfusion or prohibited medications

Observed Estimand

- Population: a subset of FAS, subjects who remain in the study through at least the visit of interest (e.g., Week 23) and have at least 1 evaluable parameter or score at target visits.
- Variable: Change from baseline at the visit of interest, or response at the visit of interest
- Measure of Intervention Effect: Mean change from baseline or proportion of subjects who respond, irrespective of transfusion or prohibited medications

5.1.4. Handling of Missing Data

Best efforts will be utilized to minimize missing values. If a subject discontinues study treatment early, the subject will be asked to complete study assessments at EOT/safety follow up visit.

For the primary endpoint, which is a composite endpoint of avoidance of transfusion and improvement of Hgb at the treatment assessment timepoint (i.e., Weeks 23, 25, and 26), missing either component results in a missing value for the endpoint. The improvement of Hgb at the treatment assessment timepoint is missing only if no Hgb value is available for all 3 visits (Weeks 23, 25, and 26). Since pre-treatment Hgb is a key requirement to enroll in the study, it is reasonable to assume that all enrolled subjects have at least 1 Hgb prior to the study treatment, which constitutes the baseline Hgb value (see [Section 5.1.1](#)).

For the primary analysis of the primary endpoint, the composite estimand is utilized. Hence, a missing value will be considered a non-response. Other sensitivity analyses specified in [Section 7.2.2](#) will be performed to evaluate the impact of missing values, when appropriate. However, other responder-type endpoints will be analyzed using observed data only.

For the analysis of continuous variables (e.g., secondary endpoints), summary statistics will be computed based on observed data. To analyze lab parameter (e.g., Hgb, bilirubin, LDH) changes attributable to the study treatment (hypothetical estimand), values post any transfusion (after Week 5) or protocol prohibited CAD treatment (defined in [Section 5.1.1](#), after Week 5) will be

censored. The mean change from baseline will be estimated using Mixed Model for Repeated Measures (MMRM) along with its 95% CIs. Multiple Imputation will also be used to estimate the mean change from baseline at treatment assessment timepoint and its associated 95% CI. All these analyses assume missing at random (MAR).

Although the assumption of MAR cannot be verified, the mechanism of missing data due to transfusion or prohibited medication use described below supports such an assumption.

- The protocol (Table 1) specifies the transfusion criteria, which is comprised of the Hgb level.
- Despite the use of prohibited medications not being allowed by the protocol, the potential need for the use of rituximab and/or combination therapy would be mostly due to the lack of response or hematologic breakthrough, which is specified in the protocol by changes in the level of Hgb and other hemolytic markers.

Therefore, the missing data due to the occurrence of transfusion and prohibited medication use is expected to be triggered by low levels of Hgb and other hemolytic markers, which are observable. Because of this mechanism, it is reasonable to assume that the probability of missing data due to transfusion or prohibited medication use is a function of the observed Hgb or other hemolytic marker levels; hence, supports the assumption for MAR.

Additional sensitivity analyses, specified in the particular endpoints, may be carried out to examine the validity of the assumption of MAR. Multiple imputation based on models compatible with Missing Not At Random (MNAR) missing mechanism may be used, where missing values at treatment assessment visit will be imputed by using Neighboring-Case Missing Value (NCMV) restriction. Certain adjustment may be needed for NCMV approach due to the small sample size, where there may be lack of neighboring cases.

Supportive analysis based on de-facto estimand will also be performed using MMRM to estimate the mean change from baseline along with its 95% CIs.

For a QOL endpoint, in the event of missing data, the total score will be estimated according to the provision for missing domains in the calculation algorithm of the score. For example, if a subject has missing data in questionnaires at a visit, the prorated FACIT-F score will be calculated, if more than 50% of items (a minimum of 7 out of 13 items) are available. Otherwise, the score is missing.

For exploratory endpoints, observed estimands will be used unless specified otherwise.

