5.2.2. Categorical Variables

Categorical variables will be summarized by counts and percentages. All percentages will be rounded to one decimal place. The percentage will be suppressed when the count is zero. Unless specified otherwise, the denominator for all percentages will be the number of subjects with non-missing data for a given summarization. This number (n) will be included with categorical summaries unless the same variable is also being summarized with descriptive statistics, in which case 'n' will already be provided.

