7.4. Exploratory Endpoints

7.4.1. Part A Exploratory Endpoints

The analysis of exploratory endpoints (listed in [Section 2.2.3](#)) will be based on Observed Estimand ([Section 5.1.3](#)). Additionally, summary of hemolytic parameters (Hgb, bilirubin, LDH, haptoglobin, and reticulocyte) over visit is added to the SAP to examine the time trend of the improvement. Unless specified below, the endpoints will be summarized by visit for continuous and categorical variables, and for time to event variables (e.g., time to obtain Hgb level of ≥ 12 g/dL) for the entire Part A.

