7.4.1.3. Time-to-Event Endpoints

Time-to-event endpoints include:

- Time to first transfusion after the first 5 weeks of study drug administration
- Time to first transfusion (including those in the first 5 weeks of study drug administration)
- Time to first normalization of bilirubin
- Time to first normalization of LDH
- Time to first normalization of haptoglobin
- Time to first normalization of Hgb level (≥ 12 g/dL)
- Time to first achieving 2 g/dL increase in Hgb level
- Time to first achieving 2 g/dL increase or normalization of Hgb level (≥ 12 g/dL)

The endpoints will be analyzed for FAS according to [Section 5.2.3](#). For subjects who receive a transfusion after Week 5, the time to normalization of lab parameters above will be censored at the time of transfusion.

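### The exploratory proportions with Hgb ≥12 g/dL and normal bilirubin, LDH and haptoglobin use observed cases only, so early leavers drop out of the denominator and a post-transfusion Hgb can count as success

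*SAP*

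**What the plan says.** Three parts of the Part A SAP together fix how these proportions are computed.

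- **Missing data.** Section 5.1.4 treats a missing primary response as non-response, then states that "other responder-type endpoints will be analyzed using observed data only". It adds: "For exploratory endpoints, observed estimands will be used unless specified otherwise". Section 7.4.1 repeats that the Part A exploratory analysis "will be based on Observed Estimand".
- **Estimand.** Section 5.1.3 defines the Observed Estimand on a subset of the FAS: "subjects who remain in the study through at least the visit of interest", with at least one evaluable value. Its measure for binary endpoints is the "proportion of subjects who respond, irrespective of transfusion or prohibited medications".
- **Denominator.** Section 7.4.1.2 lists Hgb ≥12 g/dL and normalisation of haptoglobin, bilirubin and LDH, names the FAS as the population, and refers to Section 5.2.2. There, "the denominator for all percentages will be the number of subjects with non-missing data for a given summarization".

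The list of tables in Section 12 has one output for these proportions at the treatment assessment timepoint, and it is labelled as observed. Protocol Section 4.1 keeps transfused patients in the study, so they reach Weeks 23 to 26 and supply values. It withdraws patients who need other CAD treatment in Part A and counts them as non-responders.

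**The concern.** The primary endpoint counts both early departure and transfusion from Week 5 as failure. The exploratory proportions drop the first group and ignore the second event.

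The first exclusion is unlikely to be neutral. A patient withdrawn before Week 23 for needing other CAD treatment is a primary failure but is absent from the normalisation rates. SAP 5.1.4 itself expects prohibited-drug use to arise mostly from lack of response or breakthrough, so part of the missingness is tied to poor outcome.

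The second point concerns haemoglobin. A patient transfused after Week 5 whose mean over Weeks 23, 25 and 26 is at least 12 g/dL is a primary non-responder and also a success in the Hgb ≥12 proportion.

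What is at stake is the reading of descriptive results. In a single-arm trial there is no comparator in which such a bias could cancel.

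**Working it through.** **1. The plan's own figure.** The only design figure is for the primary endpoint (Protocol 7.10, SAP 3.3): N = 20, null rate 30%, assumed rate 66%, 90% power, success from 11/20 = 55%. The exact Clopper-Pearson lower limit is 31.5% for 11/20, which passes, and 27.2% for 10/20, which fails. Power is P(X ≥ 11 | 20, 0.66) = 0.897, and the exact one-sided error is P(X ≥ 11 | 20, 0.30) = 0.017. The stated figures reproduce and do not depend on the exploratory proportions.

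**2. The same two events across the Part A SAP.**

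| Analysis | No value at Weeks 23–26 | Transfusion after Week 5 |
|---|---|---|
| Primary response (7.2.1, Table 3) | failure | failure (window Week 5 to Week 26) |
| Mean change in Hgb, bilirubin, LDH, main analysis (5.1.4, 7.3) | missing, modelled as missing at random | later values set to missing |
| Time to first normalisation (5.2.3, 7.4.1.3) | censored at last assessment if no event | censored at transfusion ("For subjects who receive a transfusion after Week 5") |
| Proportion normalised (5.1.3, 7.4.1.2) | excluded | ignored |

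The last row is the only one that neither penalises nor removes post-transfusion values.

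**3. Size of the denominator effect.** Let x be the number counted as normalised, d the number of the 20 with no Week 23–26 value, and t the number among the x who were transfused after Week 5. N = 20 is from SAP 3.3. The documents give no x, d or t; the values below are assumptions.

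- Observed-case rate = x/(20 − d)
- Rate counting these patients as failures = (x − t)/20
- With t = 0 the ratio of the two is 20/(20 − d)

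For x = 10 and t = 0:

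| d | Observed-case | All 20 | Difference (points) |
|---|---|---|---|
| 0 | 10/20 = 50.0% | 50.0% | 0 |
| 1 | 10/19 = 52.6% | 50.0% | 2.6 |
| 2 | 10/18 = 55.6% | 50.0% | 5.6 |
| 3 | 10/17 = 58.8% | 50.0% | 8.8 |
| 4 | 10/16 = 62.5% | 50.0% | 12.5 |
| 5 | 10/15 = 66.7% | 50.0% | 16.7 |

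The gap grows with x: for x = 12 and d = 4 it is 12/16 = 75.0% against 12/20 = 60.0%.

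**4. Size of the transfusion effect (Hgb).** Each such patient is worth 1/20 = 5 points. With x = 10 and d = 0, t = 1 gives 50% against 9/20 = 45%, and t = 2 gives 50% against 8/20 = 40%. Combined, x = 10, d = 2, t = 1 gives 55.6% against 45.0%.

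**5. Precision.** The exact 95% interval for 10/20 is 27.2% to 72.8%, so every observed-case figure in the table above lies inside it.

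**The case against.** The case for leaving the plan alone is substantial.

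- **Exploratory and labelled.** No hypothesis beyond the primary is tested (SAP 7.1.1). The observed-case choice is defined, assigned and printed in the table title, and 5.2.2 shows the non-missing n. This stands. It settles how serious the point is, but printing n does not give the reader the rate on all treated patients.
- **Already covered elsewhere.** The primary composite uses the same Hgb threshold, SAP 7.2.1 adds a summary of each response criterion, and disposition and transfusions are tabulated. For Hgb this largely stands: the added row would be the primary responders who reached 12 g/dL. But the component summary pools that threshold with a 2 g/dL rise, and it covers none of the other three markers.
- **Early leaving is not proof of failure.** Protocol 5.3 allows withdrawal for adverse events, pregnancy or choice. This stands: counting every leaver as not normalised gives a lower bound, not the true rate.
- **A transfused patient may still be responding to drug.** Transfusion requires Hgb below 9 g/dL with symptoms or below 7 without, so a later mean of 12 is a rise of more than 12 − 9 = 3 g/dL. The documents do not show how often donor blood would produce that. This stands too.

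A reader might also infer that donor blood flatters all four markers. The documents do not say that transfusion normalises bilirubin, LDH or haptoglobin, and normal bilirubin or LDH means a value at or below the upper limit, so a raised value counts against success. A reader might further expect the proportions to match the time-to-event results. They need not: first normalisation and status at Weeks 23 to 26 are different quantities.

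**Conclusion.** The point holds as a limited one. As written, the four proportions exclude patients without Week 23–26 data, some of whom are failures by the plan's own account, and the Hgb proportion accepts post-transfusion values. For bilirubin, LDH and haptoglobin the concern is mainly the denominator.

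The effect ranges from nothing, with no early leavers and no transfused patient counted as normalised, to 16.7 points with 10 normalised and 5 early leavers, plus 5 points on a denominator of 20 for each transfused patient counted as normalised. These counts are assumptions, so no single pair of percentages should be quoted as the expected bias.

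A reader might infer that the efficacy claim is inflated. It is not: the primary endpoint already treats these events as failure, and its conclusion, type I error and power do not change. There is also a small ambiguity to clear up, since 7.4.1.2 names the FAS while the Observed Estimand is a subset of it.

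**What to change.** Keep the observed-case row, with its n, for each of the four proportions at the treatment assessment timepoint. Beside it, add a supplementary FAS row that counts as not normalised any patient with no Week 23–26 value, or with a transfusion or prohibited CAD medication from Week 5 to Week 26. Describe that row as a conservative bound, and state both denominators in Section 7.4.1.2 and in the table.

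This is a cheap improvement: one row per endpoint, with no new data and no change to the primary analysis. The downside is that the exploratory figures become less favourable and may be conservative, because some early leavers and transfused patients may have been responding to drug.

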5.1.4.1. Mixed-effect Model for Repeated Measures

For normally distributed continuous efficacy endpoints (e.g., lab parameters), a MMRM will be used for the analysis of such endpoints at study visits (including the treatment assessment time points). The MMRM model will include the baseline value of the endpoint and visit. A heterogeneous Toeplitz (TOEPH) covariance matrix within a subject will be used. For the endpoint at the treatment assessment time points (average of Weeks 23, 25, and 26), the estimate will be calculated as the mean of MMRM estimates at Week 23, 25, and 26 visits.

Normality assumptions will be checked using graphical methods. In the event of non-normality, alternative methods will be proposed as an addendum to the SAP prior to the Part A DBL.

The pseudo SAS code for MMRM is as follows:

```
Proc mixed data=(ADaM dataset) method=reml;
  class usubjid visit;
  model chg = base visit / ddfm = kenwardroger solution;
  repeat visit / type=TOEPH subject=usubjid;
  estimate 'treatment assessment timepoint' visit 0 0 0 0 0 0 0
  0 0 0 0 0 0.333 0.333 0.333/cl;
run;
```

5.1.4.2. Multiple Imputation

The following multiple imputation procedure will be used for continuous endpoints. The regression method with monotone missing patterns will be used for the imputation step (implemented by SAS PROC MI, according to [Rubin 1987](#), pp. 166–167). The pseudo SAS code is provided to substantiate the details of the statistical approach. It does not represent runnable SAS codes for the execution of the analysis, as adjustment to the code is necessary to accommodate the data structure, variable names, and test runs.

1. For endpoints with non-monotone missing data patterns, a Markov chain Monte-Carlo (MCMC) method will first be used to fill in the intermittent missing values.

The pseudo SAS code is as follows, when the input dataset is structured such that variables chg1 - chg11 represent change from baseline at visit Week 1 (Day 7), Week 3, Week 5, Week 7, Week 9, Week 11, Week 13, Week 15, Week 17, Week 19, Week 21, and variable chg_ta represents change from baseline at treatment assessment timepoint:

```
PROC MI data=dat_in seed=1234 SIMPLE NIMPUTE=1 ROUND=1
OUT=dat_mon;
  MCMC IMPUTE=monotone;
  VAR chg1 - chg11 chg_ta;
RUN;
```

2. Missing values will be imputed as the predicted value from a regression model including explanatory variables of the number of transfusions within 6 months prior to study entry (*ntrans*), the value of the same endpoint at baseline (*base*), and change from baseline at all of the previous scheduled visits. The imputation process may be repeated sequentially starting from the earliest visit with missing value (e.g., Day 7) through the treatment assessment timepoint. The forgoing process will be repeated multiple times (i.e., B=100) to generate B imputed datasets.

The pseudo SAS code is as follows:

```
PROC MI DATA = dat_mon SEED=4321 NIMPUTE=100 out=mi_mvn SIMPLE;
  VAR base ntrans chg1 - chg11 chg_ta;
  MONOTONE METHOD=REG;
```

RUN;

- The endpoint of interest (e.g., change from baseline at treatment assessment time points) will be estimated for all B complete datasets.

The pseudo SAS code as follows:

```
PROC MEANS DATA = mi_mvn out=mi_mvn;  
  VAR chg_ta;  
  By _IMPUTATION_;  
ods output statistics=mi_est; RUN;
```

- The method of [Rubin 1987](#) will be used to combine B estimates for the overall estimate and its 95% CI.

The pseudo SAS code is as follows:

```
PROC MIANALYZE DATA = mi_est;  
  MODELEFFECTS mean;  
  STDERR;  
ods output ParameterEstimates=est;  
run;
```

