7.3. Secondary Endpoints

7.3.1. Mean Change from Baseline in Bilirubin at the Treatment Assessment Timepoint

The change from baseline in bilirubin at the treatment assessment timepoint will be analyzed for FAS excluding subjects with Gilbert's syndrome. Gilbert's syndrome status is determined by the result of the genetic test at screening. If the result of Gilbert's syndrome test is not available for a patient, the patient will be excluded from the analysis. The primary analysis will be performed according to Hypothetical Estimand (defined in [Section 5.1.3](#)), while a sensitivity analysis will be done via De-facto Estimand ([Section 5.1.3](#)). Additional details are found in [Table 4](#).

Table 4: Estimands for Change from Baseline in Bilirubin

	Hypothetical Estimand	De-facto Estimand
Population	FAS excluding subjects with Gilbert's syndrome	FAS excluding subjects with Gilbert's syndrome
Variable	Change from baseline at treatment assessment time point, where any value after transfusion and prohibited medication is considered missing	Change from baseline at treatment assessment time point
Treatment effect	Mean change from baseline, if transfusion or prohibited medications had not been available	Mean change from baseline, irrespective of transfusion or prohibited medication use

For either estimand, the mean change from baseline in bilirubin at treatment assessment timepoint, along with its 95% CI, will be estimated by the MMRM model ([Section 5.1.4.1](#)).

If the number of subjects with unknown Gilbert's syndrome status is greater than 2, additional sensitivity analysis will be performed to include such subjects (unknown Gilbert's syndrome), whose baseline total bilirubin level is low to be considered less indicative of Gilbert's syndrome.

Additional sensitivity analysis based on multiple imputation ([Section 5.1.4.2](#)) will be carried out for the Hypothetical Estimand, utilizing the regression method with monotone missing patterns. Specifically, the following 4 imputation models will be considered:

- Change from baseline in bilirubin at treatment assessment timepoint is modeled as a function of baseline bilirubin value, weight stratum (< 75 kg, >= 75 kg), and bilirubin values from Day 7 through visits Week 21, visits prior to first transfusion, or visits prior to first prohibited medication use, whichever occurs first;

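### The multiple-imputation code fills intermittent gaps once and carries that one fill into all 100 imputations; the effect is conditional and small, but the code should be corrected

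*SAP*

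**What the plan says.** Section 5.1.4.2 of the Part A SAP sets out multiple imputation in four steps.

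- **Step 1** is for endpoints with non-monotone gaps: "a Markov chain Monte-Carlo (MCMC) method will first be used to fill in the intermittent missing values". The code is "PROC MI data=dat_in seed=1234 SIMPLE NIMPUTE=1 ROUND=1". It writes one data set, `dat_mon`. Its variable list is "VAR chg1 - chg11 chg_ta", that is, eleven interim changes followed by the change at the treatment assessment timepoint.
- **Step 2** imputes what is still missing by sequential regression: "PROC MI DATA = dat_mon SEED=4321 NIMPUTE=100 out=mi_mvn SIMPLE". There is no `BY` statement. The text of this step says "The forgoing process will be repeated multiple times (i.e., B=100) to generate B imputed datasets".
- **Step 3** takes the mean in each completed data set.
- **Step 4** states that Rubin's method "will be used to combine B estimates for the overall estimate and its 95% CI".

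The section presents this as pseudo code that illustrates the approach: "It does not represent runnable SAS codes for the execution of the analysis, as adjustment to the code is necessary". The reasons given for adjustment are data structure, variable names and test runs.

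Section 7.3.1 says that MI "will be carried out for the Hypothetical Estimand, utilizing the regression method with monotone missing patterns", as an additional sensitivity analysis for bilirubin. Sections 7.3.2, 7.3.3 and 7.3.5 ask for the same for FACIT-F, LDH and Hgb. The main analysis of each of these endpoints is the MMRM.

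**The concern.** Rubin's rules measure imputation uncertainty by how far the estimate varies between completed data sets. A value that is identical in all 100 data sets contributes nothing to that variation, so it is treated as if it had been observed. Under the code as printed, this is what happens to every intermittently missing value. The pooled interval leaves out part of the uncertainty, and a different step 1 seed would give a somewhat different answer. Raising the number of step 2 draws cannot remove this.

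In addition, `ROUND=1`, read as rounding each filled value to a whole unit, is applied to every endpoint alike, including Hgb change in g/dL. At stake is how far the MI results can be trusted as a check on the MMRM for the hypothetical estimand.

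**Working it through.** The SAP states no figure for the MI variance, so there is none to reproduce. The one stated design figure, 90% power for the responder test in Section 3.3, reproduces as P(X >= 11 | n = 20, p = 0.66) = 0.897. It plays no part here.

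**1. What is left out.** Rubin's total variance is T = W + (1 + 1/B) x V, with W the average within-imputation variance, V the variance of the B estimates and B = 100. Write F for the step 1 fill and Q for the estimate from one completed data set. Across proper imputations,

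Var(Q) = E[Var(Q | F)] + Var(E[Q | F]).

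With one fill f, the 100 draws estimate Var(Q | F = f) only. The second term is absent from V. It appears instead as movement of the estimate when seed 1234 is changed.

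**2. When it matters.** The treatment-assessment change is last in the step 1 list, so it is never an intermittent gap and step 1 never fills it. The fill acts only through the predictors in the step 2 regression. If every patient has the treatment-assessment value, nothing is predicted and the fill is irrelevant. If there are no intermittent gaps, step 1 does nothing. Both conditions are needed.

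**3. Size.** Twenty patients (Section 3.3) and 12 variables (step 1 list) come from the SAP. The rest is assumed: between-patient SD about 1.7 g/dL for Hgb change, high serial correlation, 2, 5 or 10% intermittent gaps, and 0 to 3 patients without the treatment-assessment value. There were 8 data sets per scenario and 20 seeds each. The printed code (one fill, rounded, 100 draws) was compared with the corrected scheme (100 fills, one draw each). Without a ridge prior the MCMC step failed in many data sets at 5-10% gaps, so the table uses a weak one. Entries are medians over data sets; the SE ratio is formed within each data set first.

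| Gaps | Patients without endpoint | SE ratio, printed/corrected | Seed SD, printed (g/dL) | Seed SD, corrected (g/dL) |
|---|---|---|---|---|
| 2% | 1 | 1.001 | 0.023 | 0.015 |
| 2% | 2 | 0.985 | 0.039 | 0.024 |
| 2% | 3 | 0.978 | 0.042 | 0.050 |
| 5% | 1 | 1.001 | 0.025 | 0.012 |
| 5% | 2 | 0.983 | 0.050 | 0.024 |
| 5% | 3 | 0.969 | 0.055 | 0.039 |
| 10% | 1 | 0.985 | 0.028 | 0.016 |
| 10% | 2 | 0.981 | 0.064 | 0.023 |
| 10% | 3 | 0.963 | 0.064 | 0.031 |

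The median SE ratio runs from 0.96 to 1.00. In the run without the ridge prior, the 2% rows gave 0.992, 0.998 and 1.003. With no patient lacking the endpoint, the two schemes were identical (ratio 1.000, seed SD 0.000).

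**4. Cross-check.** At 10% gaps and 2 patients, the seed variance under the printed code is 0.064^2 = 0.0041, and the corrected variance is 0.500^2 = 0.25. The omitted share is about 0.0041/0.25 = 1.6%, so the SE should be short by about 1 - sqrt(1 - 0.016) = 0.8%. This is rough, since it combines medians, but it confirms that the shortfall is of the order of a percent or two.

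**5. Rounding.** A filled value moves by at most 0.5 g/dL, in predictor cells only. In the nine scenarios of the table, the Hgb estimate shifted by 0.002 to 0.015 g/dL. Rounding to whole units matters little for LDH in U/L, bilirubin in umol/L or the FACIT-F score.

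**The case against.** **The code is only pseudo code.** It is visibly not final: the `STDERR` statement in step 4 is empty, and the four imputation models in Sections 7.3.1 onward use weight stratum where this code uses prior transfusions. That stands as a reason to call this a drafting fault. It does not dispose of the point. The adjustments the SAP allows for are practical, whereas the number of fills and the rounding unit are part of the method.

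**The sentence on 100 repetitions may include step 1.** That reading is possible and would match the fix. But the sentence sits in step 2, where the code carries it out as 100 draws from `dat_mon`. Re-running step 1 with its fixed seed would also return the same fill each time. On either reading, text and code need aligning.

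**The triggering conditions are limited.** This stands. The windows in Table 1 accept unscheduled values, the treatment-assessment value needs only one of three visits, and censoring after transfusion or prohibited medication gives mainly trailing gaps. Still, the SAP provides step 1 because it expects intermittent gaps, and the hypothetical estimand itself creates missing endpoints.

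**The SE loss is not consistent.** A second simulation (20 patients, 5% gaps, 2 without the endpoint, weak ridge prior, 7 data sets, inputs again assumed) gave a mean SE ratio of 1.02. Its seed SD was 0.02-0.06 g/dL against a pooled SE of 0.32-0.52, falling to 0.01-0.02 after correction. A further small run of 14 data sets with 5% gaps and 2 censored patients gave a mean ratio of 0.936, ranging from 0.67 to 1.36 across fills, so a reader might infer a 6% understatement. That size did not replicate, and a range on both sides of 1 shows instability rather than bias in one direction. One likely contributor is the last step 2 regression: 13 predictors and an intercept on 18 patients leave 18 - 14 = 4 residual degrees of freedom, which the fix does not change.

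**Conclusion.** The code is wrong as written, and the consequence is minor. When some patients lack the treatment-assessment value and intermittent gaps also exist, Rubin's variance omits the uncertainty of the filled predictors and the estimate depends on one random fill. Under the assumed inputs the pooled SE is about 0-4% too small at the median, without a consistent direction in the second simulation. The clearer effect is dependence on the seed at 10% gaps: 0.03-0.06 g/dL, against 0.02-0.03 g/dL after correction. These figures rest on assumed missingness and variability and on few data sets; the 2% row with 3 patients even runs the other way.

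Two stronger readings are tempting. One is that every MI interval is wrong by construction. It is not, because without both conditions the two schemes coincide. The other is that rounding by up to 0.5 g/dL threatens a 2 g/dL response threshold. It does not: MI estimates a mean change, and Section 7.2.1 counts a missing primary response as non-response. The primary responder test and the MMRM are unaffected, and Section 7.1.1 plans no formal test of secondary endpoints.

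**What to change.** In Section 5.1.4.2:

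- Step 1: set `NIMPUTE=100`. Remove `ROUND=1`, or round to the precision at which each endpoint is recorded.
- Step 2: set `NIMPUTE=1` and add `BY _Imputation_`, so that each fill gets one regression draw.
- Text: state that step 1 is inside the loop of 100.

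The cost is a few option values, one `BY` statement and one sentence. No new data are needed, and the primary analysis stays as it is.

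Adding the baseline value and the number of prior transfusions to step 1, so that it matches step 2, should not be required. It would raise the MCMC model from 12 to 14 variables with 20 patients, and the 12-variable model already failed in many simulated data sets at 5-10% gaps without a ridge prior.
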